3. PATIENT SELECTION, ENROLMENT, RANDOMIZATION, RESTRICTIONS, DISCONTINUATION AND WITHDRAWAL

Each patient should meet all of the inclusion criteria and none of the exclusion criteria for this study. Under no circumstances can there be exceptions to this rule.

3.1 Inclusion criteria

For inclusion in the study patients should fulfil the following criteria:

1. Males and females:
 - a. Males must be surgically sterile or using an acceptable method of contraception (see Section 3.8.4)
 - b. Females must be of non-childbearing potential confirmed at screening by fulfilling one of the following criteria
 - a) postmenopausal defined as amenorrhoea for at least 12 months or more following cessation of all exogenous hormonal treatments and follicle-stimulating hormone (FSH) levels in the postmenopausal range,
 - b) documentation of irreversible surgical sterilisation by hysterectomy, bilateral oophorectomy or bilateral salpingectomy but not tubal ligation
2. Age ≥ 18 to ≤ 75
3. BMI ≥ 18 to ≤ 35 kg/m²
4. CAD patients, here defined as:
 - a. ACS 7-28 days prior to study randomization (ACS defined as STEMI, non-STEMI event documented by ECG, cardiac enzymes [troponin] and angiogram)
 - b. Possible post procedure LAD stenosis is $< 50\%$ and TIMI flow is ≥ 2
5. Provision of signed and dated, written informed consent prior to any study specific procedures

3.2 Exclusion criteria

Patients should not enter the study if any of the following exclusion criteria are fulfilled:

- 1 Alanine aminotransferase (ALT) >2 x ULN (i.e., above the normal range) at visit 2, cirrhosis, recent hepatitis, or positive screening test for hepatitis B (hepatitis B surface antigen) or hepatitis C
- 2 Uncontrolled Type 1 or Type 2 diabetes defined as haemoglobin A1c (HbA1c) Diabetes Control and Complications Trial (DCCT) > 9% or International Federation of Clinical Chemistry (IFCC) >74.9 mmol/mol
- 3 Patients with atrial fibrillation (chronic or current) or history of ventricular tachycardia requiring therapy for termination, or symptomatic sustained ventricular tachycardia or sick sinus syndrome or AV blockage degree 2-3
- 4 Patients with pacemaker
- 5 Prior coronary artery by-pass graft (CABG) to LAD
- 6 Left ventricle ejection fraction < 30%
- 7 Unacceptable level of angina despite maximal medical therapy or unstable angina at entry Canadian Cardiovascular Society (CCS) ≥ 3 (Visit 1 or Visit 2)
- 8 Stroke within the previous 6 months from ACS or ongoing treatment with Persantin or Asasantin
- 9 Planned treatment with zileuton, leukotriene receptor antagonists (e.g. montelukast), coumadin or steroids during trial
- 10 Planned statin therapy dose regimen changes during trial
- 11 Chronic use of anticoagulants on therapeutic dose (not including thrombosis prophylaxis) during the study
- 12 Planned additional cardiac intervention (e.g., PCI, CABG) within next 6 months
- 13 NYHA class III-IV heart failure or decompensated heart failure at discharge or hospitalization for exacerbation of chronic heart failure within the previous 3 months from ACS
- 14 Previously known severe renal disease (CKD stage 4 or 5) or previously known creatinine clearance calculated by Cockcroft Gault equation <30 ml/min*m²
- 15 Aortic or mitral valvular disease or valvular disease classified as severe
- 16 Known allergy to adenosine and mannitol, or experience of previous adverse effects of adenosine stress testing
- 17 Known elevated intracranial pressure
- 18 Heart rate < 40 bpm
- 19 Systolic blood pressure < 90 mmHg
- 20 Asthma or COPD with strong reactive component in judgment of investigator
- 21 Treatment with dipyridamole, theophyllamine, fluvoxamine, rifampicin, fenytoin or carbamazepine
- 22 Inability to comply with the study protocol
- 23 History of severe allergy/hypersensitivity or ongoing clinically important allergy/hypersensitivity to drugs with a similar chemical structure or class as study drugs

- 24 Patients unable to give their consent or communicate reliably with the investigator or vulnerable patients e.g., kept in detention, protected adults under guardianship, trusteeship, or committed to an institution by governmental or juridical order
- 25 Involvement in the planning and/or conduct of the study (applies to both AstraZeneca staff and/or staff at the study site)
- 26 Participation in another interventional clinical study with an investigational pharmaceutical product during the last 3 months also including drug eluting stents
- 27 Previous randomization in the present study
- 28 Known history or current abuse of drugs or alcohol

Procedures for withdrawal of incorrectly enrolled patients see Section 3.4.

3.3 Patient enrolment and randomization

Investigator(s) should keep a record, the patient screening log, of patients who entered pre-study screening.

The Investigator(s) will:

1. Obtain signed ICF from the potential study patient before any study specific procedures are performed
2. Assign (using the Interactive Voice Response System/ Interactive Web Response System (IVRS/IWRS)) potential study patient a unique enrolment number, beginning with 'E#
3. Determine patient eligibility. See Section 3.1 and 3.2
4. Assign enrolled patient a unique randomization code (patient number) in IVRS/IWRS at Visit 2. See Section 3.5

If a patient withdraws from participation in the study, then his/her enrolment/randomization code cannot be reused.

3.4 Procedures for handling incorrectly enrolled or randomized patients

Patients who fail to meet the eligibility criteria should not, under any circumstances, be enrolled or receive study medication. There can be no exceptions to this rule. Patients who are enrolled, but subsequently found not to meet all the eligibility criteria must not be randomized or initiated on treatment, and must be withdrawn from the study.

Where a patient does not meet all the eligibility criteria but is randomized in error, or incorrectly started on treatment, **the Investigator should inform the AstraZeneca study physician immediately, and the patient must discontinue the treatment and be**

withdrawn from the study. The AstraZeneca study physician must ensure all decisions are appropriately documented.

3.5 Methods for assigning treatment groups

At randomization the IVRS/IWRS will assign eligible patients a unique randomization code and blinded investigational product (IP) kit number(s) to the patient. Specific information concerning the use of the IVRS/IWRS will be provided in the separate user manual.

Block randomization using IVRS/IWRS will be used to randomize patients in a 6:3:4:2 ratio to receive a fixed dose of AZD5718 [REDACTED], AZD5718 [REDACTED], placebo [REDACTED] or placebo [REDACTED]. Upon completion of the randomization request form, the randomization will be produced by PAREXEL Informatics using the AstraZeneca randomization solution (AZRand).

The randomization will be stratified with type of MI as a factor (STEMI vs NSTEMI).

3.6 Methods for ensuring blinding

The study will have a single blind design. Placebo film-coated tablets will match appearance of each AZD5718 film-coated tablet strength. Identical package configuration will be used for each placebo tablets and AZD5718 tablet strength.

No member of the study team at AstraZeneca, or representative, personnel at study centres, or any clinical research organization (CRO) handling data will have access to the randomization scheme during the conduct of the study, with the exception of the PAREXEL Informatics personnel generating the randomization scheme as well as AstraZeneca Supply Chain, and the CRO companies conducting PK sample analyses, providing the IVRS/IWRS and carrying out the packaging and labelling of the study medication. This documentation will be kept in a secure location until the end of the study.

3.7 Methods for unblinding

Individual treatment codes, indicating the treatment randomization for each randomized patient, will be available to the Investigator(s) or pharmacists from the IVRS/IWRS. Routines for this will be described in the IVRS/IWRS user manual that will be provided to each centre.

The treatment code should not be broken except in medical emergencies when the appropriate management of the patient requires knowledge of the treatment randomization. The Investigator documents and reports the action to AstraZeneca, without revealing the treatment given to patient to the AstraZeneca staff.

AstraZeneca retains the right to break the code for SAEs that are unexpected and are suspected to be causally related to an IP and that potentially require expedited reporting to regulatory authorities. Treatment codes will not be broken for the planned analyses of data until all decisions on the evaluability of the data from each individual patient have been made and documented.

For the interim analysis, independent personnel with no other involvement in the study will be unblinded to certain data. A detailed description of the interim analysis including the unblinding process will be included in the interim analysis plan.

3.8 Restrictions

Restrictions for the study are listed in sections below.

AstraZeneca should be contacted if the investigator is informed of any restriction violations. AstraZeneca will decide whether a subject with restriction violation will be allowed to continue study participation

3.8.1 Medication restrictions

Abstain from taking any medications contraindicated in the study protocol. For the list of medications prohibited during the study refer to Section 7.7.

3.8.2 Dietary restrictions

- Patient should arrive at the clinic after fasting overnight (no food or liquid [except for water] intake permitted from 10 p.m. the evening before) for Visits 2, 3, 4, 4c and 5 for sampling for PK/PD and safety assessments. CFVR measurement at Visits 2, 4 and 4c requires fasting for at least 4 hours
- Abstain from use of grapefruit juice and St John's Wort during the study

3.8.3 Alcohol, Drugs of abuse, Tobacco and Caffeine Restrictions

- Prior to Visits 2, 4 and 4c, avoid intake of coffee or other caffeine containing beverages 12 hours before and until after completion of the study specific clinical assessments (CFVR, Echo)
- Abstain from tobacco/nicotine for at least 120 minutes prior to CFVR measurements, or whenever study procedures demand it. Nicotine substitutes will be offered at the discretion of the Investigator
- Abstain from alcohol for 48 hours preceding the clinical visits
- Abstain from drugs of abuse during the entire study

3.8.4 Restrictions for male study subjects

Male subjects must be surgically sterile or using an acceptable method of contraception (defined as barrier methods [condom or occlusive cap] in conjunction with spermicides) for the duration of the study (from the time they sign ICF) and for 3 months after the last dose of IP (AZD5718/matching placebo) to prevent pregnancy in partners.

Sperm Donation:

Male subjects should not donate sperm for the duration of the study and for at least 3 months after the last day of IP administration.

3.8.5 Other Restrictions

Subjects who are blood donors should not donate blood during the study and for 3 months following their last dose of AZD5718.

3.9 Discontinuation of investigational product

Patients may be discontinued from IP in the following situations:

- Patient decision. The patient is at any time free to discontinue treatment, without prejudice to further treatment
- An adverse event that, in the opinion of the Investigator or AstraZeneca, warrants discontinuation from further dosing
- Patient noncompliance that, in the opinion of the Investigator or sponsor, warrants withdrawal (e.g. refusal to adhere to scheduled visits)
- Patient is determined to have met one or more of the exclusion criteria or failed to meet all of the inclusion criteria for study participation at study entry and continuing IP, in the decision of the Investigator, might constitute a safety risk

If the patient is discontinued from IP, the scheduled study visits, data collection and procedures should continue according to the Clinical Study Protocol (CSP) until study closure. Alternatively, if the subject does not agree to this option, a modified follow up through e.g., regular telephone contacts or a contact at study closure should be arranged, if agreed to by the subject and in compliance with local data privacy laws/practices. The approach taken should be registered in the CRF.

If patient is required to or chooses to discontinue the IP, every reasonable effort should be made for the patient to remain in the study for follow-up and to complete all other study procedures until the scheduled end of the study.

3.9.1 Procedures for discontinuation of a subject from IP

At any time, patients are free to discontinue IP or withdraw from the study (i.e., investigational product and assessments – see Section 3.10), without prejudice to further treatment. A patient who decides to discontinue IP will always be asked about the reason(s) and the presence of any adverse events. If possible, they will be seen and assessed by an Investigator(s). Adverse events will be followed up (See Section 6); diary cards, and all study drugs should be returned by the patient.

If a patient is withdrawn from study, see Section 3.10.

3.10 Criteria for withdrawal

3.10.1 Screen failures

Screening failures are patients who do not fulfil the eligibility criteria for the study, and therefore must not be randomized. These patients should have the reason for study withdrawal recorded as 'Screen failure' (the potential patient who does not meet one or more criteria required for participation in a trial, this reason for study withdrawal is only valid for not randomized patients). 'Failure to meet randomization criteria' should be selected for an indication that the patient has been unable to fulfil/satisfy the criteria required for assignment into a randomized group (it is only applicable for randomized studies and should be used for patient withdrawal post-screening).

3.10.2 Withdrawal of the informed consent

Patients are free to withdraw from the study at any time (IP and assessments), without prejudice to further treatment.

A patient who withdraws consent will always be asked about the reason(s) and the presence of any adverse events (AE). The Investigator will follow up AEs outside of the clinical study.

If a patient withdraws from participation in the study, then his/her enrolment/randomization code cannot be reused. Withdrawn patients will not be replaced.

3.11 Discontinuation of the study

The study may be stopped if, in the judgment of AstraZeneca, trial patients are placed at undue risk because of clinically significant findings that:

- meet individual stopping criteria or are otherwise considered significant
- are assessed as causally related to IP,
- are not considered to be consistent with continuation of the study

Regardless of the reason for termination, all data available for the patient at the time of discontinuation of follow-up must be recorded in the CRF. All reasons for discontinuation of treatment must be documented.

In terminating the study, AstraZeneca will ensure that adequate consideration is given to the protection of the patients' interests.

4. STUDY PLAN AND TIMING OF PROCEDURES

4.1 Study Procedures

General information

For Visits 2, 3, 4, 4c and 5, patients will come to the clinic in the morning after fasting overnight (see [3.8.2](#)).

Patients will record drug intake in diary cards for out-patient administration of IP. Diary cards will be handed-out to the patients after randomization at Visit 2 and reviewed during subsequent visits and at the end of treatment (Visits 3, 4, 4b and 4c).

For the full list of assessments and sampling/measurement time points, see assessment schedule ([Table 1](#)).

Visit 1 (Screening)

Visit 1 will take place at the clinic during the in-house hospital stay post ACS-event. It should be noted that Visit 1 can last over several days. Biomarker sampling, where feasible, will take place at 1, 2, 3 and 5 days post ACS. If the patient is discharged from hospital early, he/she may be asked to come back for biomarker sampling.

- Screening of patients will be done by review of hospital medical records and by evaluation of inclusion and exclusion criteria. If a patient is found potentially suitable, he/she will be asked about participation in this study. Before any study related procedures are conducted, the patient will receive information about the study and will be asked to sign Informed Consent Form (ICF). Medical and Surgical History will be collected.
- ACS-related in-hospital invasive coronary angiogram is required to assess Thrombolysis-In-Myocardial-Infarction (TIMI) flow score from the three epicardial coronary arteries.
- Patients will be assessed for GRACE Score (Global Registry of Acute Coronary Events GRACE) - a ACS Risk Calculator that provides the percentage probability of death or death/MI at time-points up to 3 years following admission with ACS.
- Measurements and sampling for PD (u-LTE₄), safety and exploratory variables will be performed.

Visit 2 (Randomization)

- Patients will arrive at the clinic after fasting overnight and baseline sampling (PD [u-LTE₄], exploratory biomarkers and safety lab [incl. liver panels]), clinical assessments (physical examination, vital signs, and ECG) and AE-review will be conducted.
- Screening will be completed by evaluation of inclusion and exclusion criteria

- Patients will undergo baseline measurements for secondary and exploratory endpoints (cfPWV/bPWA, CFVR and echocardiography).
- Randomization and dosing will take place after baseline assessments in the morning.
- After randomization the following assessments will be conducted: PRO assessments and sampling for PK
- In case of sustained discomfort after CFVR measurement, the patient should stay at the clinic until 2 hours after status stabilization.
- IP for the first 4 weeks will be dispensed

Visit 3 (2 weeks, During Treatment)

- Visit including AE-review, clinical safety assessments, collection of samples and IP intake at the clinic

Visit 4 (4 weeks, During Treatment)

- The following assessments will be conducted during the visit: urine collection for assessment of LTE₄, sampling for PK, safety and exploratory biomarkers as well as measurement of clinical safety, efficacy and exploratory endpoints such as BP, ECG, CFVR, cfPWV/bPWA, echocardiography and PRO questionnaires
- The dose will be taken at the clinic and the patients will return the remaining IP and receive a new bottle of IP for weeks 5-8
- The patients will leave the clinic after completed measurements, but in case of sustained discomfort after CFVR measurement, the patient should stay until 2 hours after status stabilization.

Visit 4b (8 weeks, During Treatment)

- Visit including AE-review, concomitant medication review
- The patient will return the remaining IP and receive a new bottle of IP for weeks 9-12

Visit 4c (12 weeks, End of Treatment)

- The following assessments will be conducted during the visit: urine collection for assessment of LTE₄, sampling for PK, safety and exploratory biomarkers as well as measurement of clinical safety, efficacy and exploratory endpoints such as BP, ECG, CFVR, cfPWV/bPWA, echocardiography and PRO questionnaires
- The last dose will be taken at the clinic and the patient will return the remaining IP

- The patient will leave the clinic after completed measurements, but in case of sustained discomfort after CFVR measurement, the patient should stay until 2 hours after status stabilization.

Visit 5 (Follow-up)

- In the morning, urine collection for assessment of LTE₄, clinical assessments and sampling for PK, safety and exploratory biomarkers as well as measurement of clinical safety, efficacy and exploratory endpoints such as BP, ECG, cfPWV/bPWA and echocardiography.

Table 1 Study assessment schedule

	ACS event	Visit 1 Screening	Visit 2 Randomization	Visit 3 (2 weeks) During Treatment	Visit 4 (4 weeks) During Treatment	Visit 4b (8 weeks) During Treatment	Visit 4c (12 weeks) End of Treatment	Visit 5 Follow-up	Comments
Study Day	-7 days	x^a	day 1	day 14	day 28	28 days after Visit 4	28 days after Visit 4b	28 days after last dose	
Time Window		1-5 days post ACS event	7-28days post ACS event	±2	±3	±2	±3	±4 days	
Informed consent (ICF)		x							
Inclusion/exclusion criteria		x	x						
Demographic data		x							Smoking history and alcohol consumption to be included
Height		x							
Body weight ^b		x	x	x	x		x	x	
Collect date for ACS event		x							
TIMI flow score		x							
Medical and surgical history		x							
Concomitant medication		x	x	x	x	x	x	x	

Table 1 Study assessment schedule

	ACS event	Visit 1 Screening	Visit 2 Randomization	Visit 3 (2 weeks) During Treatment	Visit 4 (4 weeks) During Treatment	Visit 4b (8 weeks) During Treatment	Visit 4c (12 weeks) End of Treatment	Visit 5 Follow-up	Comments
Study Day	-7 days	x ^a	day 1	day 14	day 28	28 days after Visit 4	28 days after Visit 4b	28 days after last dose	
Time Window		1-5 days post ACS event	7-28days post ACS event	±2	±3	±2	±3	±4 days	
Serology (see Table 3)		x							
FSH and luteinizing hormone (LH) sampling (females only)		x							
Randomization			x						
Diary card hand-out			x						
Diary card review				x	x	x	x		
Diary card hand-in							x		
IP dispensed			x		x	x			
IP returned					x	x	x		
IP intake at the clinic			x	x	x		x		
Safety and tolerability:									
Adverse event (AE) review		x (SAE only)	x	x	x	x ^m	x	x	

Table 1 Study assessment schedule

	ACS event	Visit 1 Screening	Visit 2 Randomization	Visit 3 (2 weeks) During Treatment	Visit 4 (4 weeks) During Treatment	Visit 4b (8 weeks) During Treatment	Visit 4c (12 weeks) End of Treatment	Visit 5 Follow-up	Comments
Study Day	-7 days	x ^a	day 1	day 14	day 28	28 days after Visit 4	28 days after Visit 4b	28 days after last dose	
Time Window		1-5 days post ACS event	7-28days post ACS event	±2	±3	±2	±3	±4 days	
Blood pressure and pulse rate (supine)		x	x	x	x		x	x	
12-lead pECG with electronic source file		x	x	x	x		x	x	
Physical examination ^c		x	x	x	x		x	x	
Blood and urine samples for safety laboratory evaluations (including fasting glucose) ^d		x ^{e,n}	x ^f	x ⁿ	x		x	x	
Efficacy Assessments:									
Spot urine for analysis of LTE ₄ levels and urinary creatinine		x ^l	x ^g	x (pre-dose)	x (pre-dose)		x(pre-dose)	x	Screening sample will not be used for assessment of primary endpoint

Table 1 Study assessment schedule

	ACS event	Visit 1 Screening	Visit 2 Randomization	Visit 3 (2 weeks) During Treatment	Visit 4 (4 weeks) During Treatment	Visit 4b (8 weeks) During Treatment	Visit 4c (12 weeks) End of Treatment	Visit 5 Follow-up	Comments
Study Day	-7 days	x ^a	day 1	day 14	day 28	28 days after Visit 4	28 days after Visit 4b	28 days after last dose	
Time Window		1-5 days post ACS event	7-28days post ACS event	±2	±3	±2	±3	±4 days	
CFVR measurement			x		x		x		
Echocardiography			x		x		x	x	
cfPWV/bPWA			x		x		x	x	
Pharmacokinetics:									
Plasma for AZD5718			x ^h	x ⁱ	x ^j		x ⁱ	x ^k	
Exploratory Clinical Variables:									
-PRO questionnaires			x (post-dose)		x (post-dose)		x (post-dose)		
-GRACE 2.0 Score		x							
Exploratory Biomarkers:									
-Plasma for analysis of LTB ₄ levels		x ^l	x (pre-dose)	x (pre-dose)	x (pre-dose)		x (pre-dose)	x	

Table 1 Study assessment schedule

	ACS event	Visit 1 Screening	Visit 2 Randomization	Visit 3 (2 weeks) During Treatment	Visit 4 (4 weeks) During Treatment	Visit 4b (8 weeks) During Treatment	Visit 4c (12 weeks) End of Treatment	Visit 5 Follow-up	Comments
Study Day	-7 days	x ^a	day 1	day 14	day 28	28 days after Visit 4	28 days after Visit 4b	28 days after last dose	
Time Window		1-5 days post ACS event	7-28days post ACS event	±2	±3	±2	±3	±4 days	
-Blood samples for cardiovascular biomarkers		x ^l	x (pre-dose)	x (pre-dose)	x (pre-dose)		x (pre-dose)	x	
-Plasma samples to be stored in biobank for exploratory analyses		x ^l	x (pre-dose)	x (pre-dose)	x (pre-dose)		x (pre-dose)	x	
-Optional Genetic sampling			x ^o						

- a Screening during in-house stay after ACS event. Assessments can take place over several days. If the patient is discharged from hospital early, he/she may be asked to come back for blood sampling.
- b Body weight assessments to be conducted in the mornings after an overnight fast, except for non-fasting at screening (Visit 1)
- c Full physical examination at Screening (Visit 1) and at Follow-up (Visit 5), and brief physical examination on the other occasions (Visits 2, 3, 4 and 4c).
- d Fasting plasma samples for glucose measurements to be obtained after an overnight fast (from 10 p.m. the evening before) at the same time point at Visits 2, 3, 4, 4c and 5 to the extent possible.
- e Will exclude fasting glucose measurement.
- f Liver panel analyses results will be used for assessment of exclusion criteria. Samples need to be analysed as acute samples.
- g Spot urine sample to be collected in the morning prior to screening and baseline assessments.
- h Baseline sample to be obtained in the morning before screening assessments. The other sample to be taken between 1-8 h post-dose.
- i C_{Trough} sample to be collected before dose administration at 20-28 hours after previous dose (dose on day 13 (day before Visit 3) and on day before Visit 4c).
- j Sampling times: pre-dose and then 0-2 h, 2-4 h, 4-8 h post dose. Sampling will be separated with at least 1 hour.
- k One PK-sample to be collected as suitable in relation to the other follow-up measurements. Exact sampling time to be entered in the CRF.

- l Sampling, where feasible, at 1, 2, 3 and 5 days post ACS. Exact sampling time to be entered in the CRF.
- m Unscheduled safety assessments (blood and urine samples for safety lab and ECG) may be performed as judged by the investigator
- n Will exclude TSH, Free T3, Free T4 and Total T4
- o The genetic sample may be collected at any time after randomization, however, ideally samples should be collected at Visit 2

Order of assessments:

1. Spot urine sample for LTE₄ (u-LTE₄)
2. Safety labs, ECG, AE-review, physical examination and vital signs
3. Echocardiography, cfPWV/bPWA, (Vis 2, 4, 4c and 5) CFVR (Vis 2, 4 and 4c)
4. Sampling for Exploratory biomarkers and PK
5. Intake of IP
6. Meal
7. Post-dose PK sample no. 1 (Vis 2 and 4)
8. PRO (Vis 2, 4 and 4c)
9. Post-dose PK sample no. 2 (Vis 4)
10. Post-dose PK sample no. 3 (Vis 4)

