5.2.5 Vital signs

Vital signs will include pulse, and systolic and diastolic blood pressure. Vital signs will be obtained at time points indicated in Section 4, Table 1 (and ad-hoc as medically indicated).

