6.2.2 Windows

For the purpose of statistical analysis and if not otherwise specified, all the efficacy variables (primary, secondary and exploratory variables) and all the safety variables (Clinical laboratory evaluations, ECGs, Vital Signs and Physical examinations) will be assigned to the visit in which they are collected depending on the following analysis visit windows.

Analysis visit (AVISIT)	Scheduled visit day	Visit Window for Analysis (Days)
Baseline ^b	1	<]ª
Baseline Post-dose ^c	1	1
Visit 3	14	$10 - 18$ and $\leq = $ last dose
Visit 4	28	23 - 33 and <= last dose + 3
Visit 4b	56	49 – 63 and <= last dose
Visit 4c	84	74 – 94 and <= last dose + 3
Visit 5 – FUP 1 month	56 / 112	>=last dose + 24

Table 3: Visit windows

^a Includes also measurements collected at day 1 prior to first dose of IP for all variables except PRO questionnaires, ECGs, Vital Signs and Physical examinations. For PRO questionnaires, ECGs, Vital Signs and Physical examinations, all the measurements collected at day 1 will be considered as baseline measurements as per protocol. For uLTE₄ and cardiovascular biomarkers, the baseline will be the last available value before the first dose of treatment, among the values collected after the ACS event +7 days (included).

^b Analysis visit will be labelled "Baseline Pre-dose" for PK measurements.

^c Only applicable to PK measurements occurring on Day 1 after the first dose.

Measurements collected outside the visit windows will be labelled as "Unscheduled visit". For uLTE₄, urine creatinine, Creatinine-normalized u-LTE₄ and Cardiovascular biomarkers, measurements collected from date of ACS event to 6 days post ACS will be labelled as "Screening".

Distribution:

Original:

Copy:

TPCA025 Version 2 (based on TPQA036 Version 2)

STATISTICAL ANALYSIS PLAN

Sponsor:	AstraZeneca AB	Protocol/CIP Number:	D7550C00003
CIL Project Number:	40343		

In general, the baseline value used for statistical analyses is the last available value among those in the Baseline visit windows, prior to first dose of IP, except for PRO questionnaires. Additional details for baseline assessment will be given in section 6.3.

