8.8.3 Clinical Laboratory Evaluations

Clinical laboratory evaluation is performed based on the Safety Analysis Set. The list and the assessment of all Clinical Laboratory variables are reported section 6.6.3.

Laboratory test results for haematology, coagulation and clinical chemistry

Laboratory test results for haematology, coagulation and clinical chemistry will be summarized in AZ preferred units for each treatment group, and for change from baseline at each visit. Change from baseline to each post-baseline visit will be calculated as the postbaseline visit value minus the baseline visit value.

Classification of the laboratory values with respect to the normal reference range will be provided (low/normal/high). Shifts from baseline to maximum/minimum value during Ontreatment phase of this classification will be presented for each treatment group and by cohort of patients.

Hy's law criteria will also be summarized in a double-entry table by cohort of patients.

Distribution:

Original:

Copy:

TPCA025 Version 2 (based on TPQA036 Version 2) Effective Date: 27th August 2017 Prior Effective Date: 21st December 2016

Sponsor:	AstraZeneca AB	Protocol/CIP Number:	D7550C00003
CIL Project Number:	40343		

Laboratory test results for urinalysis

Laboratory test results for quantitative variables (i.e. creatinine and albumin) will be summarized in AZ preferred units for each treatment group, and for change from baseline at each visit. Change from baseline to each post-baseline visit will be calculated as the post-baseline visit value minus the baseline visit value.

Shifts from baseline to maximum value during On-treatment phase will be presented for semi-quantitative variables (i.e. albumin, protein, blood, glucose and Leukocytes). All laboratory data for haematology, coagulation, clinical chemistry and urinalysis will be also presented in listings.

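### The SAP gives Visit 4b (week 8) an analysis window for labs, vital signs and physical examinations that are not scheduled there, so any by-arm week-8 row would rest on a small, possibly selected set of unscheduled values

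*Protocol*

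**What the plan says.** **Schedule.** Protocol 4.1 describes the week-8 visit as "Visit including AE-review, concomitant medication review", plus return and dispensing of study drug. The Visit 4b column of Table 1 has no entry for safety labs, blood pressure and pulse, ECG or physical examination. Footnote m, attached to the adverse event review, adds: "Unscheduled safety assessments (blood and urine samples for safety lab and ECG) may be performed as judged by the investigator". That footnote does not mention vital signs. Their route is Protocol 5.2.5, which allows them at the Table 1 time points "and ad-hoc as medically indicated".

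**Fasting.** Protocol 3.8.2 asks patients to arrive fasted "for Visits 2, 3, 4, 4c and 5 for sampling for PK/PD and safety assessments". Visit 4b is not in that list.

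**Windowing.** SAP 6.2.2 says that, unless otherwise specified, "all the safety variables (Clinical laboratory evaluations, ECGs, Vital Signs and Physical examinations) will be assigned to the visit in which they are collected" according to Table 3. The Visit 4b entry there is "49 – 63 and <= last dose". The same section treats scheduled and unscheduled measurements alike within a window. Only values outside every window are labelled as an unscheduled visit.

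**Output.** Under SAP 8.8.3, blood labs and quantitative urinalysis are "summarized in AZ preferred units for each treatment group, and for change from baseline at each visit". SAP 8.8.4 does the same for vital signs. The SAP output list has over-time tables for labs, urinalysis, vital signs and physical examination (14.3.7.1, 14.3.7.6, 14.3.8.1 and 14.3.8.2).

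**The concern.** At Visits 3, 4 and 4c every attending patient has a planned sample, and the rule that takes the value nearest the scheduled day usually picks it. At Visit 4b there is no planned sample, so the window can be filled only by values that someone chose to obtain after randomisation. That choice may depend on earlier results or symptoms, and so possibly on treatment.

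The row would sit in the same table, under the same kind of label, as two complete visits. A reader following an arm over time could see a bump or an arm difference at week 8 that reflects only who was sampled. The variables include potential risks named in Protocol 1.3: transaminases, plasma glucose, heart rate and blood pressure. For glucose, a week-8 sample may also be non-fasting while the baseline is fasting, and it could become the on-treatment maximum in the shift table.

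**Working it through.** The plan states no figure for this point, so there is nothing to reproduce. The check traces the schedule through the windowing rule to the tables, then illustrates the size.

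**1. Does a value taken at Visit 4b fall in the window?** In Table 1, Visit 4 is day 28 ± 3 and Visit 4b is 28 days later ± 2.
- Earliest: 28 − 3 + 28 − 2 = day 51.
- Latest: 28 + 3 + 28 + 2 = day 61.

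Both lie inside days 49 to 63, so an unscheduled value at an on-time Visit 4b is labelled Visit 4b.

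**2. Who can contribute?** In the 4-week cohort the follow-up visit falls near day 28 + 28 = 56, but the condition that the value be on or before the last dose (about day 28) excludes it. Only the 12-week cohort remains: about 138 − 38 = 100 patients. Split 2:1:2 this gives 40 high dose, 20 low dose and 40 placebo, which matches Protocol 8.2.

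**3. Which outputs are by visit?**

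| Variable | Planned at 4b | Route to a 4b value | Shown by arm and visit |
|---|---|---|---|
| Blood and urine safety labs | No | Footnote m | Yes (SAP 8.8.3) |
| Vital signs | No | Protocol 5.2.5 | Yes (SAP 8.8.4) |
| Physical examination | No | None named | Over-time table (14.3.8.2) |
| ECG | No | Footnote m | No: shift to last on-treatment observation |

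**4. Illustration: sampling fraction.** Assumptions, not in the documents: a fraction f of each arm is sampled, namely those highest on a reason-for-sampling score that has correlation ρ with the lab value. With z the standard normal quantile at 1 − f, the row mean shifts by ρ·φ(z)/f standard deviations. For f = 0.10: z = 1.28, φ(z)/f = 1.755, so the shift is 0.3 × 1.755 = 0.53 to 0.5 × 1.755 = 0.88.

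| f | Patients in row (high/low/placebo) | Shift in SD, ρ = 0.3 | Shift in SD, ρ = 0.5 |
|---|---|---|---|
| 5% | 2/1/2 | 0.62 | 1.03 |
| 10% | 4/2/4 | 0.53 | 0.88 |
| 25% | 10/5/10 | 0.38 | 0.64 |
| 50% | 20/10/20 | 0.24 | 0.40 |

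With ρ = 0 the shift is zero at every f.

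**5. Illustration: ALT with no drug effect.** Assumptions: log-normal, median 0.6 x ULN, log SD σ = 0.45, correlation 0.7 between Visit 4 and week 8, and retesting only above 1 x ULN at Visit 4.
- True week-8 mean: 0.6 × exp(0.45²/2) = 0.66 x ULN.
- Threshold: z = ln(1/0.6)/0.45 = 1.135, so the share retested is Φ(−1.135) = 12.8%, or 0.128 × 40 ≈ 5 patients in a main arm.
- Row mean: 0.664 × Φ(0.7 × 0.45 − 1.135)/Φ(−1.135) = 0.664 × 0.206/0.128 ≈ 1.07 x ULN.
- Ratio: 1.07/0.66 ≈ 1.6.

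At retest thresholds of 1.5 and 2 x ULN the shares are 2.1% and 0.4%, that is 0.8 and 0.16 patients per 40. Those rows would hold about one patient or none.

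**The case against.** The best reply is that the week-8 row is an inference. The SAP lists table titles, not shells. SAP 7.1 qualifies by-visit summaries with the words *as appropriate*, so the row could be left out under the present text. The safety summaries are descriptive, they print n, and SAP 8.8.3 and 8.8.4 specify no test. A row of two to five patients between full rows would be visibly incomplete. Using unscheduled values is a deliberate rule for all post-baseline windows. All of this stands and limits the point, but nothing in the SAP requires the row to be suppressed.

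Three stronger readings are tempting, and the documents do not support them.
- **That ECG is affected in the same way.** It is windowed, but SAP 5.2 and 8.8.4 and Tables 14.3.8.4 and 14.3.8.5 show only the overall evaluation as a shift to the last on-treatment observation. There is no week-8 ECG row.
- **That week-8 labs are taken only for cause.** Footnote m leaves them to the investigator's judgement, and a site could sample routinely. Selection is possible, not established.
- **That a liver row could be inflated well beyond 1.6-fold.** Higher retest thresholds give larger ratios, but from a row that is close to empty. The intensified liver panel in the note to Protocol Table 2 also need not wait for week 8.

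On glucose, the SAP variable is defined as fasting, so a non-fasting sample is arguably not that variable. However, no rule excludes it, and the data items listed in Protocol 5.2.1 do not include fasting status.

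**Conclusion.** The point holds as a small, inexpensive correction to descriptive safety tables. For labs and vital signs, and for physical examinations if any are done, the Visit 4b window can be filled only by unscheduled values. The SAP then treats that row like a planned visit.

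How misleading the row would be cannot be fixed from the documents. It ranges from no shift, if sampling is unrelated to the value, to about 0.2 to 1.0 SD under the assumed fractions and correlations, or about 1.6-fold for ALT in the 1 x ULN scenario. It could involve only a handful of patients per arm.

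The primary and key secondary results are not touched: the u-LTE4 model uses Visits 2, 3, 4 and 4c, and the CFVR model uses Visits 2, 4 and 4c. Lab summaries at the first interim stop at Visit 4. Those at the second run to Visit 4c and share the issue (SAP 8.10.3).

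**What to change.** In SAP Table 3, remove the Visit 4b window for laboratory tests, vital signs and physical examinations. The existing rule for values outside the windows will then label them as an unscheduled visit. No windowed efficacy or safety variable is scheduled at Visit 4b, so the row becomes empty, and the SAP should say so. State that these values stay in the on-treatment maximum and minimum shifts, the Hy's Law tables and the listings. Apply the same rule at the second interim.

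Glucose taken at Visit 4b then leaves the by-visit means. Where fasting status is recorded, flag values known to be non-fasting in the shift table and listing. Do not drop them, because glucose elevation is a named risk.

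The cost is a SAP sentence and a change to the visit-assignment program. The glucose flag depends on fasting status being available, which the documents do not confirm. The downside is that unscheduled week-8 values no longer appear in the by-visit tables.
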